Therefore, we propose to develop and test a novel multi-component intervention tailored to caregiver goals, HEart failure Resilience Intervention for Caregivers (HEROIC), to improve preventive health behaviors, reduce caregiver burden and improve QOL among HF caregivers. The HEROIC intervention will include individualized, nurse-led sessions focused on a) a whole-person assessment, preventive health behaviors, personal goals, and purpose in life, b) discussion of caregiving in the context of the caregiver's identified 'purpose' which supports meaning-making and provides rationale for goal-setting to co-development of a plan to address caregiver goals to improve preventive health behaviors and/or reduce caregiver burden, and d) 'walking meetings' to model the importance of physical activity while discussing incremental action plans to help caregivers achieve goals. Because the caregiver prioritizes what matters to them, this approach will address the intersections of race, gender and financial strain by design.

The first phase of the study will be an open label pilot (N=5) followed by a single masked, two-group, randomized trial (N=44) to test the feasibility and gauge an initial effect size of the intervention. Participants will interact with study staff by phone or in-person for data collection and intervention visits, dependent on COVID-19 policies and the participants' preference. Participants will be randomized to either the immediate intervention group or the waitlist control group. In the waitlist control group, participants will receive usual care for the first 12 weeks (which is limited to printed materials provided in the clinic) and then begin the intervention. The intervention will consist of 5 individualized, nurse-led, home-based sessions, with telephone check-ins and text reminders, according to participant preference. Each participant will receive each intervention component, but interventionists will systematically tailor content to the participants' goals based on protocols. All participants will be reassessed at 12 weeks and 24 weeks by a research assistant (RA) masked to treatment condition. The primary outcome will be improvement in goal attainment of health behaviors, caregiver burden and QOL between baseline and 12 weeks. We will also examine the acceptability of the intervention using intervention compliance and participant satisfaction data.

2. Objectives

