Aim 1: Test intervention components through an open label pilot (N=5) of the intervention, followed by in-depth interviews. We will assess the salient features of the novel intervention components using mixed methods including examination of all quantitative measures and qualitative interviews to explore acceptability, participant/interventionist interactions, home environment factors, goal achievement and perceived value of intervention. Intervention components will be adapted for the trial participants (who will be randomized) based on results of Aim 1.

Aim 2: Conduct a single-masked, waitlist control pilot trial of the HEROIC intervention (N=44). We hypothesize that caregivers who receive the intervention will have improvement in primary outcomes (goal attainment of health behaviors, caregiver burden and QOL) and potential mechanisms (self-efficacy and heart rate variability, a biomarker of resilience) between baseline to 12 weeks (immediate intervention group) and 12-24 weeks (waitlist).

Aim 3: Assess the salient features of the intervention components and delivery using mixed methods to explore acceptability, participant/interventionist interactions, home environment factors, goal achievement and perceived value of the intervention.

3. Background

There are five significant gaps in the science of HF caregiving. First, most caregiving interventions focus on conditions like dementia, which have a predictable trajectory; HF is characterized by unpredictable exacerbations. Second, HF caregiver studies have included predominantly white, middle income caregivers. Third, current HF caregiver interventions often place additional responsibility on the caregiver and have a deficit-focus instead of a strengths-based approach. Pourth, there is a dearth of interventions that decrease emotional distress and improve preventive health behaviors of HF caregivers. Fifth, trialed interventions have had limited impact. In addition, the National Academies have called for research to meet the needs and values of diverse family caregivers and to improve caregiver health. Therefore, the purpose of this study is to improve preventive health behaviors, caregiver burden and QOL in caregivers of patients with HF through a resilience-building intervention delivered in the home (HEROIC).

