This study is grounded in a strong theoretical basis using principles of Bandura's Theory of Self-Efficacy and the Society to Cells Resilience Model. ^{28,29} Our theoretically-driven proposal posits that contextual, caregiver and patient factors influence caregiver self-efficacy, and resilience, ^{28,29} Resilience, or positive adaptation when facing stressors, can be increased through person-centered interventions through incremental action plans to achieve goals, which can also increase self-efficacy. ^{5,30,31} Such interventions improve biomarkers of stress resilience such as heart rate variability which is related to CVD risk and self-reported outcomes such as caregiver burden and QOL. ^{32–34} In addition, articulating 'purpose in life' promotes resilience, placing the stressor in the context of larger values. ^{14,35–37} Based on these tenets, the conceptual framework ties together the many proposed levels of measurement such as context, self-efficacy, resilience, health behaviors, caregiver burden and QOL by intervening simultaneously on them to improve overall resilience (figure 1). **This flips the paradigm of caregiver intervention from a burden and difficulty focus to a strength-building and resilience focus.**

4. Study Procedures

Overview of Study Design (Figure 2): We propose an open label pilot (n=5) with a subsequent single-blind, two group randomized pilot trial to test the feasibility and gauge an initial effect size of the HEROIC intervention to improve QOL. The immediate intervention group (n=22) will receive the intervention during weeks 0-12. The waitlist control group (n=22) will be provided written materials with community resources for caregivers during the first 12 weeks, then they will begin the intervention. Waitlist control groups are used to first provide an untreated comparison and second to allow wait-listed participants an

Figure 2. Group assignment and outcome measurement

opportunity to receive the intervention at a later date.^{38,39} This is especially appropriate given that very few services are currently offered to HF caregivers. To account for estimated 20% attrition we will recruit 49 participants.

Using the NIH Stage Model for Behavioral Intervention development, this proposal is congruent with a Stage 1A and 1B level of development.⁴⁰ Development of the intervention will be made more person-centered and

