| Week 10 | Discuss how caregiver will involve social support in next goals |
| | Walking meeting (if virtual: suggest participant take a walk during call) |
| Phone Check-in | Review/edit purpose statement |
| Week 12 | Assess goal attainment and strategies to achieve goal |
| | Walking meeting (suggest participant take a walk during call) |
| Data Collection Visit | Heartrate Variability Measurement |
| Week 12 | Survey |
| Data Collection Visit | Heartrate Variability Measurement |

Week 24 Survey

Death of the Patient: If the patient/care recipient of the enrolled caregiver/study participant dies during the study, we will send a sympathy card. In that communication, we will ask the caregiver if they would like to participate a modified version of the intervention for bereavement: 1-3 visits (scheduled every other week) with a nurse for bereavement support within two months of the death of the care recipient. Additional instrumental support resources will be suggested such as grief support groups, referral to Roberta's House and bereavement resources for tasks to complete after someone you love dies. If the caregiver chooses to discontinue their participation, we will discontinue study contact and data collection. Data from caregivers whose care recipient dies will be excluded from analysis of primary and secondary outcomes.

Research Variables and Measurement

We chose measures (Table 2) based on previous RCT experience of mentors as well as those that met the following criteria: 1) possess known reliability and validity with ethnically diverse samples; 2) are sensitive to change from an intervention; 3) have clinical relevance; 4) Common Data Elements to connect this work with the broader literature and 5) represent objective as well as subjective indicators of the domains we seek to impact. Finally, we sought to achieve a balance between psychometric quality and practical considerations such as respondent burden. All instruments with the exception of demographics will be measured at baseline, 12 and 24 weeks. Patient characteristics will be obtained from chart review.

^{*} Waitlist control group will begin intervention at week 12.

Table 4: Constructs, Instruments and Reliability

| Theoretical Construct | Instruments and variables | Cronbach's alpha | | | |
|--|--|---------------------|--|--|--|
| | Contextual Factors | | | | |
| | 1)How well does the amount of money you have take care | | | | |

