Generalized estimating equations (GEE) will be used to examine the difference between intervention and waitlist groups in change from baseline to 12 and to 24 weeks for QOL (primary outcome). Time, group and the group by time interaction will be included in the model. We will also calculate Hedges' g for differences in change over time between the groups in change in primary outcomes. Hedges' g is recommended over Cohen's d' to correct of an upward bias in small sample sizes.⁸⁵ The effect size associated with the variables will be compared to established clinically significant improvement reported in the literature, rather than placing emphasis on statistical significance.

b. Secondary outcome variables.

Generalized estimating equations (GEE) will be used to examine the difference between intervention and waitlist groups in change from baseline to 12 and to 24 weeks for self-efficacy and HRV (secondary outcomes) using a similar approach (as described for primary outcome).

In addition, the correlation between the change in the mechanisms and change in primary outcomes will be examined. We will also examine cost of the intervention.

Mixed Methods Analysis - Qualitative analysis and joint displays will be used to compare those with improvement in quantitative outcomes after the intervention to those who did not have improvement to elucidate unmeasured or unpowered change as reported by participants. This mixed methods analytic approach to intervention evaluation maximizes what we will learn from the pilot by increasing understanding of context, responsiveness to ethnically and culturally diverse populations and how implementation influences outcomes. Thus, the development and testing of the HEROIC intervention will address preventive health behaviors of HF caregivers, using rigorous methods to

promote inclusivity and tailor the intervention to caregiver needs to decrease caregiver burden and improve quality of life.

c. Statistical plan including sample size justification and interim data analysis.

Sample Size:

Aim 1) For our open-label pilot we will include 5 caregivers to test intervention components, feasibility, acceptability, delivery and communication.

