Aim 2) As a pilot study, the analyses will not have adequate power to detect significant differences. Therefore, initial effect sizes, rather than statistical significance, will be examined for evidence of the effectiveness of the intervention. With a target sample size of 44, 22 in the waitlist control and 22 in the intervention, we will be able to gauge an initial estimate of the effect size associated with the intervention as compared to usual care for caregivers. Waitlist control groups are used to first provide an untreated comparison and second to allow wait-listed participants an opportunity to receive the intervention at a later date. ⁸⁷ This is especially appropriate given that very few services are currently offered to HF caregivers. We will also conduct debriefing interviews with all participants following the trial. To account for an estimated 20% attrition, we will recruit a total of 49 to the trial with the goal of 44 participants completing the study.

Understanding the factors that predict which intervention components are successfully implemented and for which participant subgroups will be critical for fine-tuning this multicomponent intervention for future proposals that will extend efficacy examinations and effect modification analyses. Acceptability of the intervention will be examined in multiple ways. We will examine percentages of people who stayed in each arm of the study and conduct numerous descriptive correlational analyses of the association between the intervention compliance and other variables. These analyses will quantify intervention implementation by demographic and participant health variables. Analyses that utilize the post-randomization data (e.g., treatment compliance) ⁴⁰⁻⁴³ will be evaluated in supplementary analyses. We will distinguish non-compliance with intervention from attrition or loss to follow-up, i.e., missing data. We will also use the participant satisfaction data to examine acceptability of the intervention.

d. Early stopping rules.

As this is a low-risk behavioral intervention pilot, we have not defined any early stopping rules.

8. Risks

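### The stated 20% attrition, 49 recruited and 44 completing cannot all hold: at 20% attrition, 49 recruits are expected to give about 39 completers

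*Combined protocol and SAP*

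**What the plan says.** Section 7, part c (Sample Size, Aim 2) builds the size statement on 44 people: "With a target sample size of 44, 22 in the waitlist control and 22 in the intervention". The same paragraph then sets recruitment: "To account for an estimated 20% attrition, we will recruit a total of 49 to the trial with the goal of 44 participants completing". Here 44 counts completers.

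Section 4 (Overview of Study Design) repeats the allowance: "To account for estimated 20% attrition we will recruit 49 participants". It also attaches 22 to each group as the number who receive their assigned condition: "The immediate intervention group (n=22) will receive the intervention during weeks 0-12", with the same n for the waitlist group. The study overview before section 2, and Aim 2 in section 2, give 44 as the N of the randomised trial without saying whether it means randomised or completing.

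The open-label phase is sized separately under Aim 1: "For our open-label pilot we will include 5 caregivers to test intervention components". No section gives another attrition figure or shows how 49 was obtained.

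**The concern.** An attrition allowance should carry the recruited number to the target number. Here it does not: the stated loss rate applied to the stated recruitment gives fewer people than the stated goal. The figure 44 is also used in two ways, as trial size and as completers. If all 49 recruits are randomised, the groups would start at about 24–25, not 22.

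Two things depend on this. First, the plan relies on 22 + 22 for its initial effect-size estimate, and under its own attrition figure that number is not expected to be reached. Second, retention is itself a result: section 7 will use the percentage staying in each arm as evidence of acceptability. If 39 of 49 complete, the present text does not say whether that is what was expected (20% loss) or a shortfall (39 against 44).

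**Working it through.** **Inputs.** Attrition 20%, 49 recruited, 44 completing and 22 per group (section 7, part c, Aim 2; 20% and 49 also in section 4). Open-label pilot 5 (section 7, part c, Aim 1).

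**Trying to reproduce 49 from 44 at 20%.**
- Usual inflation, N/(1 − d): 44/0.80 = 55.
- The common but incorrect N × (1 + d): 44 × 1.20 = 52.8, rounded up to 53.
- By group from 22, rounding up: 22/0.80 = 27.5, so 28 × 2 = 56; or 22 × 1.20 = 26.4, so 27 × 2 = 54.

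None of these gives 49.

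**Running it forwards.** 49 × 0.80 = 39.2 expected completers, and 39.2/2 = 19.6 per group. The shortfall against 44 is about 5.

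**What attrition 49 and 44 imply.** 1 − 44/49 = 5/49 = 10.2%. A 10% allowance does reproduce the figure: 44/0.90 = 48.9, rounded up to 49, and 49 × 0.90 = 44.1.

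**Chance of reaching the goal.** With X ~ Binomial(49, 0.80), P(X ≥ 44) = 0.0547, about 5.5%. This assumes independent dropout.

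**Effect on precision.** The plan gives no precision figure, so this is an added approximation for a two-group standardised difference near zero, SE = √[(n₁ + n₂)/(n₁n₂)]:

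| Completers | SE | 1.96 × SE | J = 1 − 3/(4·df − 1) | 1.96 × J × SE |
|---|---|---|---|---|
| 22 + 22 | 0.3015 | 0.591 | 0.9820 (df 42) | 0.580 |
| 20 + 19 | 0.3204 | 0.628 | 0.9796 (df 37) | 0.615 |

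With or without the small-sample factor J, the ratio is 1.06, so the interval is about 6% wider.

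**Alternative source of 49.** 5 open-label + 44 randomised = 49. There would then be no attrition allowance, and 44 × 0.80 = 35.2, so about 35 would be expected to complete.

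**The case against.** The strongest reply is that 49 is simply the study total, 5 + 44. Section 4 introduces both phases before giving 49, and does not tie that number to the randomised trial. But the Aim 2 paragraph does say the 49 are recruited to the trial, and the five are sized separately under Aim 1. Nor would this reading rescue the plan: it removes the allowance altogether and enlarges the shortfall. It stands as a point to confirm before the text is changed, because it affects what the correction costs.

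A second reply is that 44 is only a goal, in a pilot that disclaims power. It is true that 44 comes from no power or precision calculation and that the loss of precision is small. That limits the weight of the point. It does not make the sentence right, because 49 is presented as the number that allows for 20% loss.

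A third reply is that recruited is not the same as randomised. Consent precedes the baseline visit and randomisation follows it, so some may be lost in between. Stratified allocation with no blocking described also does not guarantee an even split. Both are fair: 24–25 per group is approximate and assumes all 49 are randomised.

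Finally, which figure to change is the sponsor's decision. That is so, and the documents do not show which of the three is mistaken.

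**Conclusion.** The concern holds. Taken together, 20%, 49 and 44 are arithmetically inconsistent, and nothing else in the documents reconciles them. Under the stated attrition about 39 completers are expected from 49, not 44; under the stated 49 and 44 the attrition is about 10%.

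The error is definite but its consequence is modest: an approximate half-width for Hedges' g of 0.63 rather than 0.59 (0.62 rather than 0.58 with the small-sample correction), with no power claim affected. It should be fixed, but it does not threaten the trial.

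The conclusion takes the 49 to exclude the open-label five; if they are included, the shortfall is larger. The figures count completers, not people analysed. Section 4 (Death of the Patient) says "Data from caregivers whose care recipient dies will be excluded from analysis of primary and secondary outcomes", which lowers the analysed number, and the plan does not say whether the 20% covers this. In the other direction, GEE can use week-12 data from people lost later.

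**What to change.** First confirm that the 49 excludes the five open-label caregivers and that all 49 are to be randomised. Then keep recruitment at 49 and adopt one of two sets of text.

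**(A) If 20% is the real expectation.**
- Section 7, part c, Aim 2: replace the 22 + 22 clause with *With 49 caregivers randomised (24–25 per group) and about 39 (19–20 per group) expected to complete*. Replace the attrition sentence with *We will recruit 49 caregivers to the randomised trial, not counting the five in the open-label pilot. With an estimated 20% attrition, about 39 are expected to complete the study.*
- Section 4: use the same attrition sentence, and change each n=22 to *24–25 randomised, 19–20 expected to complete*.
- Study overview and Aim 2 in section 2: change N=44 to *N=49 randomised, about 39 expected to complete*.

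**(B) Only if the sponsor does expect 44 of 49 to finish.** The 10% is back-calculated and appears nowhere in the documents.
- Section 7, part c, Aim 2: change the 22 + 22 clause to *With a target of 44 completing, 22 in each group*. Change the attrition sentence to *With an estimated 10% attrition, we will recruit 49 caregivers to the randomised trial, not counting the five in the open-label pilot, with the goal of 44 completing the study.*
- Section 4: use the same attrition sentence, and change each n=22 to *24–25 randomised, 22 expected to complete*.
- Study overview and Aim 2 in section 2: change N=44 to *N=49 randomised, 44 expected to complete*.

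**Cost.** If 49 excludes the five, both are wording changes and add no participants, visits or payments. Under (A) the stated goal drops from 44 to about 39; under (B) the attrition assumption becomes less cautious. If 49 turns out to include the five, neither text fits as it stands. Adopting one would raise the randomised number from 44 to 49 and total enrolment to 54, adding 5 caregivers, 5 × 5 = 25 core sessions and 5 × 3 × $50 = $750.

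Keeping both 20% and 44 completers would need 55 recruits. That is 6 more caregivers, 6 × 5 = 30 core sessions and up to 6 × 3 × $50 = $900, before phone check-ins and any tablets. It is not needed for this correction.
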